### **3.2 | Allocation**

Patients were randomly assigned to the intervention and control groups respectively in line with the inclusion criteria of sampling through a computerized randomization system. Patients reached in the pre-application period (n = 6) were also included in the sample of the study, considering possible patient loss throughout the study. Ultimately, 66 patients were included in this study; the subjects were individually numbered and randomized by an individual outside of the investigation team using the website software program Research Randomizer

(<http://www.random.org>) to divide the subjects into the intervention group (33 patients) and control group (33 patients). The patients were not blinded. If someone declined, the next patient from the list was invited instead.

### **3.3 | Sample size**

The sample of the study was determined by power analysis with the help of NCSS-PASS 2014 software. The study findings of Naylor et al. (2004) determine the standard deviation rate ( $\pm 1,3$ ) with a 90% confidence level and a tolerance rate of 0.1%; each group consisting of 30 people,  $n=60$  (Julious, 2009; Zar, 1984). The study began with a pre-application process for the first six patients. Since there is no difference between the forms used during the pre-application process and no problem was encountered in the maintenance process, the pre-application group was included in the study.

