### **Aim of the study and hypotheses**

The purpose of this study is to evaluate the effectiveness of the Nurse Led Transitional Care Model. The hypotheses are as follows;

H0: Nursing care carried out in collaboration with a multidisciplinary team in line with TCM for elderly patients who have undergone open heart surgery has no effect on decreasing the patients' functional autonomy, their quality of life levels and the rate of repeated post discharge referrals to hospital and rehospitalization.

H1: Nursing care carried out in collaboration with a multidisciplinary team in line with TCM for elderly patients who have undergone open heart surgery may improve the patients' functional autonomy, their quality of life levels and decrease the rate of repeated post discharge referrals to hospital and rehospitalization.

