### **3.6 | Statistical methods**

The data obtained throughout the study were evaluated by statistical analyzes (using IBM SPSS Statistics 23 software). Parametric tests were leveraged while evaluating research data based on the argument of Law of Large Numbers stating that (İnal & Günay, 2002) “The average of the results obtained from a large number of trials  $n \rightarrow \infty$  will tend to become closer to the expected value”. The evaluation of the research data provides frequency distribution (number, percentage) for categorical variables and descriptive statistics (mean, standard deviation) for numerical variables. Difference between categorical variables with two groups was tested using Independent t-Test whereas the difference between the categorical variables with more than two groups was tested with "One Way Variance Analysis" (ANOVA). Following the analysis; initially, the homogeneity of the variance was controlled by Levene Test and then the group or groups causing the difference were controlled by "Multiple Comparison Test". The difference between the groups regarding the variables that provide variance homogeneity was evaluated via Bonferonni while Tamhane's T2 test was used to examine the difference between groups in variables that do not comply with variance homogeneity. In addition, the difference between the two numerical variables over time was evaluated with Dependent Sample t Test while the relationship between the two categorical variables was examined with the Chi-Square test. Statistical significance was considered as  $p < 0.05$ .

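### Three or four outcomes carry H1 at p < 0.05 each with no primary and no claim rule; separately, the 30 per arm cannot be checked from its stated inputs

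*Combined protocol and SAP*

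**What the plan says.** **Outcomes and claim.** In the section on aims and hypotheses, H1 is that care under the model for patients after "open heart surgery may improve the patients" in respect of "functional autonomy, their quality of life levels and decrease the rate of repeated post discharge referrals to hospital and rehospitalization". No section ranks these outcomes or names one as primary. Section 3.5 places the two scales at admission and nine weeks after discharge, and the referral and rehospitalisation check at six months.

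**Testing.** Section 3.6 sets one threshold for all tests: "Statistical significance was considered as" p < 0.05. Its only multiplicity device is a post-hoc step after ANOVA with more than two groups: "The difference between the groups regarding the variables that provide variance homogeneity was evaluated via Bonferonni", with Tamhane's T2 where variances differ. Numerical variables over time get a paired t-test, and "the relationship between the two categorical variables was examined with the Chi-Square test". Sidedness is not stated.

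**Sample size.** Section 3.3 calls its method a power analysis. It takes an SD of 1.3 from an earlier study and gives the size "with a 90% confidence level and a tolerance rate of 0.1%; each group consisting of 30 people". Section 3.2 adds six patients, "considering possible patient loss throughout the study", and randomises "to divide the subjects into the intervention group (33 patients) and control group (33 patients").

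**The concern.** A reader of the results needs to know beforehand what would count as evidence that the care model works. Here one significant result out of three or four could be presented as support for H1, and nothing in the plan rules that out. A within-arm change over time, which section 3.6 also tests at 0.05, could be presented in the same way, although patients recovering from surgery may change in both arms.

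The sample-size paragraph does not help. It ties the SD of 1.3 to no outcome of this trial and states no difference to detect, so it does not show which outcome the trial was built around. Its 90% confidence level also does not obviously match the 0.05 in section 3.6.

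**Working it through.** **1. False-claim rate under an any-one rule.** Inputs: alpha 0.05 per test (section 3.6); three outcomes in H1, or four if referral and rehospitalisation are counted separately; no true effect on any outcome. The any-one rule is an assumption, because the plan gives no rule.

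- Independent tests: 1 − 0.95³ = 0.143; 1 − 0.95⁴ = 0.185.
- Correlated tests: equicorrelated normal statistics, two-sided, with the correlation assumed.

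| Correlation | Any one at 0.05, three / four tests | Holm over all, three / four tests |
|---|---|---|
| 0 | 14.3% / 18.5% | 4.9% / 4.9% |
| 0.5 | 12.5% / 15.6% | 4.5% / 4.3% |
| 0.8 | 9.8% / 11.4% | 3.5% / 3.2% |

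Under an all-outcomes rule the false-claim rate does not exceed 5%. The price is power: three independent outcomes with 80% power each give 0.8³ = 51%.

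**2. Does the Bonferroni/Tamhane step cover this?** No. It locates differences among more than two groups for a single variable. The trial has two arms, so the step does not arise in the arm comparison and makes no adjustment across outcomes.

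**3. Can 30 per arm be reproduced?** Inputs given: SD 1.3, 90% confidence, tolerance 0.1%. Not given: outcome, difference, sidedness, and any figure labelled as power. The number cannot be derived from these inputs alone, so a difference has to be assumed. With n per arm = 2(z₁ + z₂)²SD²/δ²:

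- Assumed δ = 1.0, one-sided 0.05 (for this purpose the same as two-sided 0.10), 90% power: 2 × (1.6449 + 1.2816)² × 1.69 / 1 = 28.95, so 29. The noncentral t gives power 0.894 at 29 and 0.903 at 30, so 30 is the exact minimum.
- Assumed δ = 1.1, two-sided 0.05, 90% power: 2 × (1.9600 + 1.2816)² × 1.69 / 1.21 = 29.35, so 30.

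Different unstated inputs therefore lead to the same 30. In the first case, 90% confidence would be a two-sided alpha of 0.10 and the tolerance a garbled beta of 0.1. That reading is an assumption.

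**4. What 30 per arm can detect.** Two-sample t-test, two-sided, noncentral t, in SDs of the score compared between arms:

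| Alpha | 80% power | 90% power |
|---|---|---|
| 0.05 | 0.74 | 0.85 |
| 0.0167 (Holm first step, three) | 0.86 | 0.97 |
| 0.0125 (Holm first step, four) | 0.89 | 1.00 |

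With all 33 per arm analysed at 0.05, the figures are 0.70 and 0.81 SD. An effect of 0.736 SD has 80.0% power at 0.05, 65.0% at 0.0167 and 60.8% at 0.0125 with 30 per arm. None of this applies to outcomes compared as proportions.

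**The case against.** **H1 joins its outcomes with a conjunction.** Read strictly, all must improve, and then nothing is inflated. This stands as far as it goes. A reader might infer that the trial has a false-claim rate of 10% to 19%; the documents do not support that as a fact, because it depends on an any-one rule that they never state. But they do not state the all-outcomes rule either, and section 3.6 describes separate tests with one threshold.

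**No arithmetic error is shown in 3.3.** This also stands. A reader might treat the tolerance as a margin of error, find that 1.3 and 0.1 call for a far larger sample, and conclude that 30 is wrong or too small. The documents do not support that: section 3.3 calls the calculation a power analysis, the tolerance has no defined meaning or unit, and an unstated difference of about 1.0 gives exactly 30. The missing inputs may lie in the sources that section 3.3 cites. The fault is incomplete reporting.

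**Testing may have been planned one-sided.** H1 is directional, and a one-sided 0.05 would reconcile section 3.3 with section 3.6. The fix should therefore not override a one-sided plan that can be documented.

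**The study is described as already carried out** (section 1). That limits what can be repaired: a detectable-effect sentence added now does not recover the design basis. It does not remove the need to say which results support a claim.

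**Conclusion.** The main point holds. H1 rests on three or four outcomes, none is primary, each is tested at 0.05, and no rule says when H1 is supported. Under an any-one rule the false-claim rate is 14.3% / 18.5% for three / four independent tests, and 9.8% / 11.4% at correlation 0.8. Further quality-of-life scores used for claims would raise it. The size depends on the assumed rule and correlations; the absence of a rule does not.

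The secondary point is narrower: 30 per arm is uncheckable. Section 3.3 needs its real inputs and an alpha that agrees with section 3.6. Two-sided alpha 0.10 would not match 0.05 there unless testing in 3.6 is one-sided.

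**What to change.** **Section 3.6.**

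- State that claims of effect rest only on the between-arm comparison of each outcome: week 9 for the two scales, six months for referral and rehospitalisation. Label the within-arm paired t-tests as descriptive.
- State whether referral and rehospitalisation are one outcome or two, and name the quality-of-life score or scores tested.
- Apply Holm across these outcomes at an overall two-sided 0.05 (first step 0.05/3 = 0.0167 for three, 0.05/4 = 0.0125 for four). Count every quality-of-life score on which a claim is made; more scores make the first step stricter.
- If a dated document that predates the data fixes one-sided testing or a single primary outcome, follow and cite it. A primary chosen later must be labelled post hoc and does not restore error control.

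**Section 3.3.** Replace the sentence on confidence and tolerance with the inputs actually entered in the software: outcome, difference, SD and the outcome it belongs to, alpha, sidedness and power. Reconcile that alpha with section 3.6. If the inputs cannot be recovered, say so. Then add: *For a continuous score compared between arms by a two-sample t-test at two-sided 0.05, 30 per arm detects a difference of 0.74 SD of that score with 80% power or 0.85 SD with 90% power. This does not apply to referral or rehospitalisation compared as proportions.*

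**Cost.** Wording in two sections and no extra patients. The price is power at Holm's first step: 80% becomes 65% for three outcomes or 61% for four, with 30 per arm. Later Holm steps are less strict. The sample-size statement will also read less favourably than it does now.

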### **3.4 | Ethical considerations**

A permission dated 25.05.2017 and No: 2017/42 was obtained from the University Clinical Research Ethics Committee for the implementation of the study. Furthermore, in order for the study to be carried out in the university hospital, necessary written permits were obtained from General Directorate of Turkish Public Hospitals, General Secretariat of the Provincial Public Hospitals Association, Head Physician and Nursing Services Department of the University Hospital in question. Written permission was obtained from the authors via e-mail for the scales used in the research. Verbal and written consent was obtained from the patients included in the study.

### **3.5 | Intervention**

Patients in intervention group were given care based on the 'Nurse Led Transitional Care Model Protocol' (Figure 2) until the post discharge 9th week starting from date of hospitalization. Patients in control group were given standard care services.

The patients in both groups were interviewed face-to-face by the Researcher (Coordinator Nurse) in the first twenty-four hours following their admission to the hospital and administered "Introductory Information Form", "The Functional Autonomy Measurement System" and "SF-36 Quality of Life Scale". In addition, the Researcher (Coordinator Nurse) reached the patients in both groups after nine weeks following their discharge and reapplied the "The Functional Autonomy Measurement System" and "SF-36 Quality of Life Scale". Six months following their discharge these patients were called by phone and checked up on their repeated referrals to hospital and/or rehospitalization.

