| 
Coordinator Nurse:
 
 
✓ Home visit within 24 hours after hospital discharge; 
 
• The patient's living conditions,
 
• Understanding and executing the proposed treatment and drug regimen,
 
• Assessment of the performance on executing practices to accelerate the recovery of the patient
 
• To continue planning and executing healthcare services
 
 
 
✓ Providing consultancy service via telephone to the patient and family members within post discharge first week
 
   |   |  |   |
| 
Coordinator Nurse:
 
 
✓ Home visits at post discharge 2nd and 6th weeks; 
 
• "Post-Discharge Home Follow-Up Form of Elderly Person Undergoing Open Heart Surgery"
 
• "Post-Discharge Recurrent Hospital Admission Follow-Up Form"
 
• Providing training and consultancy in cooperation with the team members for the detected problems
 
• Follow-Up for the detected problems
 
 
 
   |   |  |   |
| 
Coordinator Nurse:
 
 
✓ Home visits at post discharge 9th week; 
 
• "Post-Discharge Home Follow-Up Form of Elderly Person Undergoing Open Heart Surgery"
 
• "Post-Discharge Recurrent Hospital Admission Follow-Up Form"
 
• Providing training and consultancy in cooperation with the team members for the detected problems
 
• Follow-Up for the detected problems
 
• 'The Functional Autonomy Measurement System',
 
• 'SF-36 Quality of Life Scale'
 
 
 
 |   |  |   |
| 
Coordinator Nurse:
 
 
✓ Telephone Communication at post discharge 6th month 
 
• "Post-Discharge Recurrent Hospital Admission Follow-Up Form"
 
 
 
   |   |  |   |

**Figure 2.**'Nurse Led Transitional Care Model Protocol'

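### The nurse who delivers the intervention also administers both outcome scales, with no blinded assessor described, and the conditions of measurement and the capture of rehospitalisation differ by arm

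*Combined protocol and SAP*

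**What the plan says.** **Who measures.** Section 3.5 gives both measurements of both scales to one person. At admission, "The patients in both groups were interviewed face-to-face by the Researcher (Coordinator Nurse) in the first twenty-four hours following their admission". At follow-up, "the Researcher (Coordinator Nurse) reached the patients in both groups after nine weeks following their discharge and reapplied the" same two scales.

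**Who treats.** In Figure 2 the Coordinator Nurse makes daily ward visits, trains patients, coordinates care, makes home visits and advises by telephone ("Providing consultancy service via telephone to the patient and family members within post discharge first week").

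**Conditions at week 9.** For the intervention arm, Figure 2 has an entry headed "Home visits at post discharge 9 th week". It contains "Providing training and consultancy in cooperation with the team members for the detected problems", follow-up of those problems, an admission follow-up form and both outcome scales. For controls, section 3.5 says only that they were reached; neither place nor mode is given.

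**Hospital use.** Section 3.5: "Six months following their discharge these patients were called by phone and checked up on their repeated referrals to hospital and/or rehospitalization". The caller is not named. Figure 2 lists the 6-month call under the Coordinator Nurse, and also schedules the admission follow-up form at weeks 2, 6 and 9, for the intervention arm only.

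**Blinding.** Section 3.2: "The patients were not blinded". Assessor blinding is not mentioned anywhere, and the limitations in section 4 do not raise it.

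**The concern.** A nurse who delivers the intervention necessarily knows who received it. By week 9 the intervention patients are answering questions from someone who has trained and visited them since admission; no such relationship is described for controls. Social desirability in the answers, and any lean in how the interview is conducted, would then differ by arm. The difference in setting adds to this: even an impartial interviewer would be measuring one arm during a supportive home visit and the other in circumstances that the plan does not describe.

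The independent t-test in section 3.6 compares means. It cannot separate a difference in how the scales were obtained from a difference caused by the care model. At stake is whether a significant result on functional autonomy or SF-36 could be read as an effect of the intervention.

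For rehospitalisation the issue is unequal opportunity to record an event, so the comparison may partly reflect how often patients were asked.

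**Working it through.** The plan states no size for this bias and has no figure of its own to reproduce. The check has two parts.

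**1. False-positive rate on the scales under an assumed shift**

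Inputs from the plan: 33 patients per arm (section 3.2), independent t-test and significance at p < 0.05 (section 3.6). Assumptions: two-sided test (sidedness is not stated), true effect zero, equal SDs, and a shift of *b* SD in the intervention arm caused by measurement alone.

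- Degrees of freedom: 2 × 33 − 2 = 64; critical value t = 1.998.
- Non-centrality: λ = b / √(2/33) = 4.062 b.
- False-positive rate: P(|T| > 1.998), where T is non-central t with 64 df and parameter λ.

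| Assumed shift b (SD) | λ | Rate per test, 33 per arm |
|---|---|---|
| 0 | 0 | 5.0% |
| 0.1 | 0.406 | 6.9% |
| 0.2 | 0.812 | 12.6% |
| 0.3 | 1.219 | 22.5% |
| 0.4 | 1.625 | 36.0% |
| 0.5 | 2.031 | 51.6% |

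Nearly all these rejections favour the intervention (at 0.2 SD, 12.3 of the 12.6 percentage points). The expected difference reaches the significance threshold at b = 1.998 × √(2/33) = 0.49 SD. With the 30 per arm planned in section 3.3, the rates at 0.2, 0.3 and 0.5 SD are 11.9%, 20.8% and 47.8%, so some loss to follow-up changes little.

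**2. Ascertainment of hospital use, by arm**

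| Occasion after discharge | Intervention (Figure 2) | Control (section 3.5) |
|---|---|---|
| Week 2 | Admission follow-up form at home visit | None described |
| Week 6 | Admission follow-up form at home visit | None described |
| Week 9 | Admission follow-up form at home visit | Scales reapplied; no admission form described |
| Month 6 | Telephone call, same form | Telephone call |

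That is four occasions against one. If the interim forms feed the outcome, intervention patients have less chance of forgetting an event, which would raise their count and work against the intervention. Reluctance to report events to the treating nurse would work the other way. The plan does not say whether the interim forms count, so the net direction cannot be determined. The t-test figures above do not apply to this outcome.

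**The case against.** The case against has several parts, and some of them stand.

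- **A reader might infer that this nurse scores every outcome.** The text supports less. It says that she administered and reapplied the two scales; it does not say who scored them. For the 6-month call, section 3.5 names no caller, and Figure 2 names her only within the intervention protocol.
- **A reader might infer from Figure 2 that training comes before the scales at week 9,** because the scales are listed last. It is an unnumbered list, and position does not establish sequence. What stands is that no sequence is fixed.
- **A reader might infer that all the bias favours the intervention.** That is plausible for the two scales. It does not hold for rehospitalisation, where closer follow-up could find more events in the intervention arm.
- **The magnitudes are generic.** This is fair: they describe any t-test with 33 per arm, and nothing in the documents says which shift applies. At 0.2 SD, about 87% of null tests would still be non-significant, and roughly half an SD is needed before a false positive is more likely than not.
- **A small, single-centre study without funding may have no second assessor.** This is reasonable, and the changes proposed do not require one. Nor do the documents show that these changes would remove most of the bias.
- **A self-completed, sealed SF-36 would take the nurse out of the interview.** It is a trade-off, not a clear gain: patients are aged 60 and over, the inclusion criteria require only spoken Turkish, and missing forms could be selective.

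**Conclusion.** The concern holds for the two scales and, in a different form, for rehospitalisation. It is explicit that the intervention nurse administers both scales in both arms, and that the intervention arm's week-9 scales belong to a visit that includes training. The plan describes neither a blinded assessor nor the mode of the control assessment. That the nurse is unblinded is an inference, but a necessary one.

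The consequence is a risk of unknown size. Under the assumptions above, a shift of 0.2 to 0.3 SD would multiply the per-test error rate by about 2.5 to 4.5 (12.6/5 and 22.5/5), while 0.1 SD would add about two percentage points. The documents do not show that a false positive occurred or is likely. For hospital use the arms are not ascertained alike, and the direction of any bias is open.

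**What to change.** Using existing staff:

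1. **Week-9 scales.** Administer both before any training, consultancy or problem follow-up, by one stated mode that is feasible in both arms, with the admission scores not to hand.
2. **Hospital use.** Count repeated referrals and rehospitalisations from discharge to month 6 from the hospital record for all patients, supplemented by the same scripted 6-month call in both arms. Do not count events found only on the interim forms used in the intervention arm.
3. **Reporting.** State as a limitation that both scales were administered unblinded by the nurse who delivered the intervention.

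The cost is mainly revised data-collection instructions. The common mode needs thought, because section 4 already cites transportation limits, so it should be one that can be delivered to controls as well. The hospital record misses admissions elsewhere, which the call only partly covers. The protocol describes the study in the past tense; if the week-9 data are already collected, steps 2 and 3 are what remain, with step 2 limited to the record and to what the 6-month call captured in each arm. None of this removes the bias entirely, because patients and nurse remain unblinded.
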